Appendix 2-7 References	

1 Protocol Summary

Title:	Autologous Conditioned Plasma (ACP) Intra-Articular (IA) Injections for Knee Osteoarthritis (OA):
Study Design:	This study is a prospective, multicenter (up to 5 sites), randomized, double blind, two-arm study. Ninety (90) patients will be randomized to receive a three single weekly intra-articular (IA) injection of either ACP (n=60) or Phosphate buffered saline (n=30). To evaluate the effectiveness of ACP (three weekly doses IA of 3-6 ml of ACP injected into the knee from baseline through 6 months) to treat Knee OA. Subjects will remain blinded to treatment throughout the study.
	All patients will have a screening visit and three treatment visits one week apart (visit 2/Week 0, visit 3/Week 1, and Visit 4/Week 2), followed by four follow-up visits; Visit 5/2 months (60 days), Visit 6/3 months (90 days) and Visit 7/6 months 180 days) after the 1st treatment visit.
	Patients will have a follow-up visit at Visit 8/12 month (365 days) after the 1 st treatment visit. Note: Once the last patient has reached their 6 month (180 days) Visit, an analysis of the primary endpoint will be performed based on 6-month outcomes.
	All subjects will continue to be followed out to 12 month (365 days) post-treatment. When the last patient reaches the 6-month time point, all available data will be reported to FDA.
Investigational Arm:	ACP Treatment: Three IA injections of 3-6 mL ACP at 1-week intervals.
Control Arm:	Three Normal Saline IA injections of 3-6 mL at 1-week intervals.
Primary Endpoint:	Change in WOMAC Pain score from baseline to 6 months.
Primary Hypotheses:	ACP treatment is superior to control in terms of mean change from baseline to 6 months (180 days) in the WOMAC Pain score.
Study Success Criterion:	This study will be achieve its study success criterion if it is demonstrated that the mean improvement in WOMAC Pain score from baseline to 6 months (180 days) is significantly larger for ACP treatment compared to saline control with a 1-sided $p \le 0.025$.

Conditional Endpoint:	If superiority in WOMAC Pain score improvement is established, the study is designed to provide additional evidence of superiority in terms on improvements in WOMAC Function score from baseline to 6 months (180 days).		

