3.4.1 Inclusion Criteria

- 1. The subject is ≥ 18 to 70 years of age.
- 2. The subject present with complaints of continued pain of primary knee for at least 6 weeks.
- 3. The subject has documented radiographic evidence of OA in the tibio-femoral or patella-femoral compartment of the target knee (Kellgren-Lawrence Grades II-III), using radiographs performed within 24 weeks of screening.
- 4. The subject has a WOMAC pain score of at least 8 out of 20 and at least moderate pain (a score of 2) for at least 2 questions on activities

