3.4.2 Exclusion Criteria

- 1. Grade I and IV on the target knee Kellgren-Lawrence grading scale
- 2. Subject has clinically 3+ effusion of the target knee (stroke test grading system).
- 3. Subject has significant $(> 10^{\circ})$ valgus or varus deformities as evidenced by standard of care X-ray.
- 4. Subject has had systemic or IA injection of corticosteroids in any joint within three months prior to screening.
- 5. Viscosupplementation in any joint in the past six months.
- 6. Subject which, in the investigator's opinion, has an increased risk for postprocedure bleeding (e.g., bleeding disorder or taking anticoagulants except low-dose aspirin).
- 7. Subject had prior open surgery on the target knee within 12 months or knee arthroscopy within 6 months
- 8. Subject has inflammatory disease of either knee other than OA.
- 9. Subject which, in the investigator's opinion, has underlying medical conditions that could interfere with the evaluation of the outcome.
- 10. Subject with positive pregnancy test, or breast feeding.
- 11. Subject with plans to participate in other clinical trial involving medical or surgical intervention in the next 12 months.
- 12. Subject with any condition (including cognitive impairment) that, in the opinion of the investigator, might interfere with the evaluation of the study objectives.
- 13. Subject has rheumatoid arthritis or gout
- 14. Subject has a history of or a current infection at the affected joint.
- 15. Subject with plans to undergo any elective orthopedic surgery in the next 12 months.
- 16. Subject requires pain management therapy (with the exception of acetaminophen) not related to the target knee.

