Appendix 2-6 Case Report Forms

ACP_Pivotal_Test Visit Date at Visit 1 - Screening,Visit 2 - Day 0,Visit 3 - Week 1 (+/- 3 days),Visit 4 - Week 2 (+/- 3 days),Visit 5 - 2 months (+/- 7 days),Visit 6 - 3 months (+/- 7 days),Visit 7 - 6 months (+/- 14 days),Visit 8 - 1 year (+/- 30 days),Unscheduled

Visit Date Now

3. The subject has documented Radiographic evidence of OA in the tibio-femoral or patella-femoral compartment of the target knee (Keligren-Lawrence Grades II-III), using radiographs performed within 24 weeks of The subject present with complaints of continued pain of primary knee for at least 6 weeks. O Symptomatic OA of the patella-femoral compartment of the target knee C Symptomatic OA of the tibio-femoral compartment of the target knee 3a. Which knee is a candidate for the ACP procedure? The subject is >= 18 to 70 years. 3c. Date of Radiograph 3b. Specify indication: **ORight OLeft** CYes CNo CYes CNo Oves ONo screening.

Arthreet double syringe ide

4. The subject has WOMAC pain score of at least 8 out of 20 and at least moderate pain (a score of 2) for at least 2 questions on activities.

CYes CNo

1. Grade I or IV on the knee Keligren-Lawrence grading scale C Yes C No
2. The subject has clinically apparent 3+ effusion of the target knee (stroke test grading system) C Yes C No
3. The subject has significant > 10° Valgus or Varus deformities as evidence by standard of care X-ray C Yes C No
 Subject has had systemic or IA injection of corticosteroids in any joint within three months prior to screening. O Yes O No
5. Viscosupplementation in any joint in the past six months. C Yes C No
6. Subject has an increased risk for post-surgical bleeding (e.g., bleeding disorder or taking anticoagulants except low-dose aspirin). C Yes C No
7. Subject had prior open surgery on the target knee within 12 months or arthroscopy within 6 months. O Yes O No
8. Subject has inflammatory disease of either knee other than OA. O Yes O No
9. Subject with any condition medical conditions that could interfere with the evaluation of the outcome. C Yes C No
10. Subject with positive pregnancy test, or breast feeding C Yes C No
11. Subject with plans to participate in other clinical trial involving medical or surgical intervention in the 12 months. CYes CNo
12. Subject with any condition (including cognitive impairment) that, in the opinion of the investigator, might interfere with the evaluation of the study objectives. O Yes O No

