08. Injection was given at the soft spot between patella and femur C Yes

CNo

Specify:

09. What was the volume of treatment injected?

10. Were there any device complications during the IA procedure $\ensuremath{\mathbb{C}}\xspace$ Yes

C No

If Yes, specify

Unable to pull up outer syringe

Unable to pull up inner syringe

Damaged

Cracked

Packaging - Device/component missing

Packaging - Broken in package

Leaking

Air mixed with blood

Piece broke from device

Frozen

Other

~	-	~	-1	£	
5	p	е	CI	τy	2

Series I Kit Part #	Lot #	Quantity Used:
IDE-ABS-10011		
11. Were there any Adv	erse Events during	procedure?

CYes (complete AE form)

C No

WOMAC Scoring: 0=none, 1=mild, 2=moderate, 3=severe, 4=extreme

For each WOMAC @ dimension, a subscale score is calculated by simple summation: Pain = 0-20 Stiffness = 0-8 Physical function = 0-68

Section A PAIN

Think about the pain you felt in your knee caused by your arthritis during the last 48 hours.

QUESTION: How much pain have you had...

ONone OMIId OModerate OSevere OExtreme when walking on a flat surface?

ONNO OMID OMODERATE OSEVERE OEXTREME 2. when going up or down stairs:

3. at night while in bed? (that is - pain that disturbs your sleep) ONONE OMIId OMODERATE OSevere OExtreme

CNone CMild CModerate CSevere CExtreme 4. while sitting or lying down?

ONone OMId OModerate OSevere OExtreme while standing?

Section B STIFFNESS

Think about the stiffness (not pain) you felt in your knee caused by the arthritis during the last 48 hours. Stiffness is a sensation of **decreased** ease in moving your joint.

How severe has your stiffness been after you first woke up in the morning? ONONE OMIId OMODERATE OSEVERE OExtreme ف

7. How severe has your stiffness been after sitting or lying down or while resting later in the day? ONONE OMIId OMODELATE OSEVERE OEXTREME

DIFFICULTY PERFORMING DAILY ACTIVITIES Section C

Think about the difficulty you had in doing the following daily physical activities caused by the arthritis in your knee during the last 48 hours. By this we mean **your ability to move around and take care of yourself**.

QUESTION: How much difficulty have you had ...

8. when going down the stairs?	WOMAC 8 C	CAL
ONone OMild OModerate OSevere OExtreme		
9. when going up the stairs?	WOMAC9 C	AL
C None C Mild C Moderate C Severe C Extreme	WOMAC10	CAL
10. when getting up from a sitting position?		
ONORE O Mild O Moderate O Severe O Extreme	WOMAC11	CAL
11. while standing?		

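### The WOMAC form and the pain-severity entry criterion do not name the injected knee, so some primary-endpoint scores could describe the other knee

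*Combined protocol and SAP*

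**What the plan says.** The Protocol Summary gives the primary endpoint as "Change in WOMAC Pain score from baseline to 6 months". The WOMAC form in Appendix 2-6 introduces each section with a stem that mentions a single knee but no side:

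- Pain: "Think about the pain you felt in your knee caused by your arthritis during the" last 48 hours.
- Stiffness: "Think about the stiffness (not pain) you felt in your knee caused by the arthritis during the" same period.
- Function, the conditional endpoint: "Think about the difficulty you had in doing the following daily physical activities caused by the arthritis in your knee during the" same period.

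Inclusion 4 in Section 3.4.1 reads "The subject has a WOMAC pain score of at least 8 out of 20", with a further condition on individual items, and names no knee. The description of the WOMAC (Section 3.7), the visit procedures (Sections 6.2.1, 6.3.1 to 6.3.3), the schedule of events (Appendix 2-1) and the WOMAC score-entry form do not tie the questionnaire to the study knee.

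Other parts of the plan do identify the knee. The eligibility form asks "Which knee is a candidate for the ACP procedure" and records left or right (item 3a). The treatment form records the procedure side. The visit form asks about extra therapy for the target knee. Inclusion 3 and exclusions 1, 2 and 7 refer to the target knee (exclusion 7 for open surgery).

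No criterion excludes osteoarthritis or pain of the opposite knee as such. Exclusion 8 covers inflammatory disease in either knee but leaves OA aside. Exclusion 16 reads "Subject requires pain management therapy (with the exception of acetaminophen) not related to the target knee".

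**The concern.** A patient with two painful knees may answer the WOMAC for either knee, for the worse one, or for both together. If the score describes the uninjected knee, it carries no local treatment effect. If the knee being rated changes between screening and Month 6, the change score and the baseline covariate in the MMRM no longer refer to the same joint.

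The same gap affects entry. A patient whose study knee is only mildly painful could reach 8 out of 20 because of the other knee.

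The ambiguity cannot be resolved afterwards. No form shown records which knee was rated or whether the opposite knee hurts, and source verification of the WOMAC cannot recover a side that was never specified.

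**Working it through.** **Who can enter with a painful opposite knee.**

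- Inclusion 2 requires at least six weeks of pain in the target knee (Protocol Summary) or primary knee (Section 3.4.1). It sets no severity; severity comes only from inclusion 4.
- Exclusions 4 and 5 remove patients with a recent steroid injection or viscosupplementation in any joint. Exclusion 15 removes those with elective orthopedic surgery planned.
- Exclusions 9 and 12 depend on the investigator's opinion and do not mention the opposite knee.
- Exclusion 16 removes patients who need more than acetaminophen for something other than the target knee. The eligibility form as reproduced in Appendix 2-6 lists only 15 exclusions, so this one is not captured there.
- Section 6.1.1 calls for films of both knees, but no criterion uses the opposite film to exclude OA.

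A patient with OA in both knees, managed with acetaminophen or nothing, passes all of these unless the investigator decides otherwise.

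**The plan's own sample size.** Inputs from Section 8.4.1: effect size d = 0.80, one-sided alpha 0.025, 2:1 allocation, two-sample t-test, 52 + 26 = 78 evaluable patients for 90% power, raised by 15% to 90.

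Power comes from the noncentral t with df = n₁ + n₂ − 2 and noncentrality d / √(1/n₁ + 1/n₂).

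- 52 + 26: 0.80 / √(1/52 + 1/26) = 0.80 / 0.2402 = 3.33, power 90.8%.
- 50 + 25: power 89.7%.

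So 78 is the smallest 2:1 total that reaches 90%, and 78 × 1.15 = 89.7, giving 90. The plan's figure reproduces.

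**Illustration of dilution.** Let f be the share of scores that describe the uninjected knee. Assume those scores carry no treatment effect and the SD is unchanged. The effect size is then 0.80 × (1 − f). The documents give no value for f; the range below is an assumption.

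| f | Effect size | Power, 78 evaluable | Power, 90 evaluable | Power, 78 evaluable, if the true undiluted effect is 1.235 |
|---|---|---|---|---|
| 0 | 0.80 | 90.8% | 94.3% | 99.9% |
| 10% | 0.72 | 84.1% | 89.0% | 99.5% |
| 20% | 0.64 | 74.9% | 80.8% | 98.2% |
| 30% | 0.56 | 63.4% | 69.7% | 94.4% |

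The value 1.235 is the pilot-based effect size (4.2 / 3.4) that Section 8.4.1 reduces to 0.80.

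**Sensitivity to the SD assumption.** A mixture of responding and non-responding scores widens the spread in the ACP arm. With ACP variance 1 + f(1 − f) × 0.80² and a normal approximation, power at 78 evaluable goes from 85.0% to 84.4% at f = 10%, from 75.9% to 74.5% at 20%, and from 64.5% to 62.6% at 30%. The constant-SD assumption therefore matters by no more than about 2 percentage points.

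**The case against.** The strongest reply is that the setting supplies what the form omits. The study knee is chosen at eligibility, that knee is injected three times, and staff ask about it at follow-up visits. Most patients would probably take a singular knee to mean that one. Site training may also cover the point, and a header on the patient WOMAC may have been lost in the reproduction of the form, although the separate score-entry form keeps its title and shows no side. This makes a low share plausible. It does not make the instruction part of the plan.

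Three stronger readings are tempting, and the documents do not support them.

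- A reader might infer that patients can qualify with a painless study knee, so that the pain enrichment fails. Inclusion 2 rules that out. Only the severity threshold can be met by the other knee.
- A reader might infer that attention moves to the opposite knee mainly in patients helped by ACP, so that the loss falls on the ACP arm. This is a plausible mechanism, but nothing in the documents shows it.
- A reader might take the power figures as a forecast. They lean high. A patient who rates the study knee at baseline and a milder opposite knee at Month 6 still shows a fall, and part of the effect can remain. Full loss applies to patients who rate the opposite knee throughout.

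The reduction from 1.235 to 0.80, made to allow for bias in the pilot, also leaves room if the true effect is nearer the pilot's. If the pilot used the same form in similar patients, its result already contains some dilution; the documents do not say.

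**Conclusion.** The gap is real. Neither the patient-facing instrument for the primary endpoint nor the severity criterion names the injected knee, and a painful osteoarthritic opposite knee is not excluded. Inclusion 2 and exclusions 4, 5, 9, 12, 15 and 16 narrow the group at risk without closing it.

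The consequence is bias toward no difference: some loss of power and an understated effect, with no inflation of type I error. Its size is unknown. The power losses in the table are an upper-end illustration that rests on an assumed share and on zero effect in every misdirected score. The point justifies a cheap correction to the forms. It does not show that the trial is underpowered, and it gives no reason to change the sample size.

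**What to change.** - Mark the study side, left or right as recorded in item 3a, on every WOMAC, including the one at screening. Have the patient answer all three sections for that knee, and state this in Sections 6.2.1 and 6.3 as well as on the form.
- Word inclusion 4 as the WOMAC pain score of the target knee, in the Protocol Summary, Section 3.4.1 and the eligibility form.
- Optionally, add one yes/no item at screening on pain in the opposite knee and report it as a descriptive baseline characteristic. A subgroup analysis on it would be imprecise with about 90 patients at 2:1.

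The cost is one instruction line on an existing form and, if wanted, one extra item. Visits and sample size do not change. Some patients who would have qualified on the other knee become screen failures; the documents give no basis for saying how many. The gain for Function is only partial, because many of its items are whole-person tasks that depend on both knees.
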